9. RESEARCH METHODS

9.1. Study Design

[figure not shown]
This structured secondary data collection study will be a retrospective, cohort design to describe concomitant vaccine uptake and subsequent outcomes during one influenza vaccination season. Individuals will be indexed on the date of their first Pfizer-BioNTech mRNA bivalent COVID-19 or influenza vaccine. Exposure groups will be assigned as follows:

- Group 1: Same day (Pfizer-BioNTech mRNA bivalent COVID and flu on the same day);
- Group 2: COVID alone (Pfizer-BioNTech bivalent COVID only);
- Group 3: flu alone (influenza vaccine of any type only).
- CCI

A one year lookback period prior to the index vaccination will be used to identify covariates. Individuals will be followed starting 15 days after vaccination until experiencing one of the following: 1) outcome 2) disenrollment 3) receipt of a second vaccine of the same type 4) receipt of the other vaccine or any type of COVID-19 vaccine 5) end of data or 6) death. Only Pfizer-BioNTech mRNA bivalent COVID-19 vaccine will be assessed. All types of influenza vaccines recommended for the eligible population will be eligible for inclusion, but for the 65+ age group only enhanced influenza vaccines will be included.

PFIZER CONFIDENTIAL

Figure 1. Overall Study Design

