9.2.1. Inclusion Criteria

Patients must meet all of the following inclusion criteria to be eligible for inclusion in the study:

1. Enrolled in Optum claims database as of 31 August 2022 (date bivalent authorized).
2. Has a Pfizer-BioNTech mRNA bivalent COVID-19 or influenza vaccine (any type) between 31 August 2022 and 30 January 2023 (earliest vaccine is index date).
3. Aged ≥ 18 years on the index date.
4. 365 days of continuous enrolment prior to index date.

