9.2.2. Exclusion Criteria

Patients meeting any of the following criteria will not be included in the study:

1. Patients with a second dose of any type of bivalent mRNA COVID-19 or flu vaccine, disenrolled or died within 14 days following the first dose.
2. Has prior COVID-19 diagnosis (U07.1, any setting, any position) within 90 days (per CDC guidance¹² on length of time before receiving a vaccine) before and on index.
3. Has influenza vaccine between 01 August -30 August 2022 (before study period).

PFIZER CONFIDENTIAL

4. Has a COVID-19 or influenza diagnosis code in any setting within 14 days after index vaccination (excluded from all cohorts).
5. For patients 65+, had a standard dose influenza vaccine or unknown type influenza vaccine.
6. Has Moderna mRNA bivalent COVID-19 vaccine or monovalent vaccine of any type on index date.

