9.3. Variables

9.3.1. Exposure

Table 1. Vaccination Status Variables		
Variable	Role	Operational definition
Group 1: Same Day (Concomitantly administered Pfizer-BioNTech COVID-19 mRNA bivalent vaccine + influenza vaccine)	Exposure	
Patients meeting the following criteria will be included in the Same Day cohort:
 
1. NDC or CPT codes for both the Pfizer-BioNTech mRNA bivalent COVID-19 vaccine and an influenza vaccine during the study period.2. The first Pfizer-BioNTech mRNA bivalent COVID-19 vaccine and influenza vaccine NDC or CPT codes during the study period occurred on the same date.3. No influenza vaccine NDC or CPT code between 01 August 2022 and 30 August 2022. 
If the patient receives >1 mRNA bivalent COVID-19 vaccine or influenza vaccine during follow-up, the patient is censored on the date of the NDC or CPT code for the second vaccine of the same type. mRNA bivalent COVID-19 and influenza vaccine NDC and CPT codes are listed in Appendix Table 1.

Group 2: COVID alone (COVID-19 mRNA bivalent vaccine alone)	Exposure	
Patients meeting the following criteria will be included in the COVID-19 alone cohort:
 
1. Pfizer-BioNTech mRNA bivalent COVID-19 vaccine NDC or CPT code during the study period and no influenza vaccine on that date.2. No influenza vaccine NDC or CPT code between 01 August 2022 and 30 August 2022. 
If the patient receives >1 mRNA bivalent COVID-19 vaccine (any type) during follow-up or an influenza vaccine, the patient is censored on the date of the NDC or CPT code for the second mRNA bivalent COVID-19

PFIZER CONFIDENTIAL

Table 1. Vaccination Status Variables

Variable	Role	Operational definition
		vaccine/influenza vaccine. mRNA bivalent COVID-19 vaccine NDC and CPT codes are listed in Appendix Table 1 .

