Group 3: Flu alone (Influenza vaccine alone)	Exposure	
Patients meeting the following criteria will be included in the Flu alone cohort:
 
1. Influenza vaccine NDC or CPT code during the study period and no mRNA bivalent COVID-19 vaccine on that date.2. No influenza vaccine NDC or CPT code between 01 August 2022 and 30 August 2022. 
If the patient receives >1 influenza vaccine or an mRNA bivalent COVID-19 vaccine (any type) during follow-up, the patient is censored on the date of the NDC or CPT code for the second influenza vaccine/COVID-19 vaccine. Influenza vaccine NDC and CPT codes are listed in Appendix Table 1.

CCI		[REDACTED]

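### Another brand's bivalent dose given before an index influenza vaccine is not screened out of Flu alone, which may slightly dilute the all-cause hospitalization HR for Same day versus Flu alone

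*Combined protocol and SAP*

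**What the plan says.** All references are to the combined protocol and SAP.

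- **Index date (9.1, 9.2.1).** Only a Pfizer-BioNTech bivalent or an influenza vaccine sets it: "between 31 August 2022 and 30 January 2023 (earliest vaccine is index date". A Moderna bivalent dose does not.
- **Exclusion 6 (9.2.2).** It removes a person who "Has Moderna mRNA bivalent COVID-19 vaccine or monovalent vaccine of any type on index date".
- **Flu alone (9.3.1, Table 1, Group 3).** Criterion 1 is "Influenza vaccine NDC or CPT code during the study period and no mRNA bivalent COVID-19 vaccine on that date". Criterion 2 is a look-back, but for influenza vaccine only. It matches exclusion 3: "Has influenza vaccine between 01 August -30 August 2022 (before study period".
- **After index.** Table 1 says that on a second influenza vaccine "or an mRNA bivalent COVID-19 vaccine (any type) during follow-up, the patient is censored". Section 9.1 ends follow-up on "receipt of the other vaccine or any type of COVID-19 vaccine", and Table 3 counts any mRNA bivalent brand as a censoring vaccine. Exclusion 1 also looks forward only, over the 14 days after the first dose.
- **Group label (9.1).** "Group 3: flu alone (influenza vaccine of any type only".
- **Same day (Table 1, Group 1).** "The first Pfizer-BioNTech mRNA bivalent COVID-19 vaccine and influenza vaccine NDC or CPT codes during the study period occurred on the same date". This too leaves an earlier dose of another brand unscreened.
- **Adjustment (9.3.4, 9.7).** Table 4 has a modelled covariate for any COVID-19 vaccine in the previous year, with three levels: 60 days or less (Recent), 61 to 365 days (Older), and none. It enters the propensity score. Variables that remain imbalanced are added to the outcome model.
- **Models (9.7).** For Same day versus Flu alone, the visible outcomes are all-cause hospitalization and the influenza endpoints.

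**The concern.** The plan treats an other-brand bivalent dose as disqualifying on the index date and as a reason to censor afterwards, but does not look for it before index. An earlier Pfizer-BioNTech bivalent dose cannot cause this problem, because it would itself set the index. The gap is therefore specific to other brands.

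All-cause hospitalization in Group 1 versus Group 3 is meant to contrast both vaccines with influenza vaccine only. If some of the comparator already has a current-season bivalent dose, and that dose lowers hospitalization, the contrast shrinks. The influenza endpoints, the Group 1 versus Group 2 comparison and Objective 1 give no comparable reason for concern.

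**Working it through.** **1. One dose at three times.** Take a Moderna bivalent dose in a person whose first qualifying vaccine is an influenza vaccine.

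| Timing of the dose | Rule that applies | Result |
|---|---|---|
| 31 August 2022 to the day before index | none visible | stays in Flu alone, not censored |
| Index date | exclusion 6; Group 3 criterion 1 | excluded |
| Follow-up | Table 1, Table 3, section 9.1 | censored |

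**2. How far the covariate reaches.** Follow-up starts on day 15 and data end on 14 February 2023.

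| Index date | Unscreened days | In Recent | In Older | Follow-up starts | Potential follow-up |
|---|---|---|---|---|---|
| 30 October 2022 | 60 | 60 | 0 | 14 November 2022 | about 92 days |
| 30 November 2022 | 91 | 60 | 31 | 15 December 2022 | about 61 days |
| 30 January 2023 | 152 | 60 | 92 | 14 February 2023 | about 1 day |

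Up to an index of 30 October 2022 (31 August + 60 days), every affected dose is in Recent. Later, some fall in Older, but those patients have less follow-up. Both levels pool bivalent with monovalent doses. The one valency-specific item in Table 4, a monovalent dose between 1 July and 30 August 2022, is descriptive only.

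**3. Dilution before weighting.** The documents give neither the affected share f of Group 3 nor the true all-cause HR, so both are assumed. With rare events, equal baseline hazard and affected people carrying Group 1's hazard:

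observed HR = HR / ((1 − f) + f × HR)

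| True HR | f = 1% | 2% | 5% | 10% | 20% |
|---|---|---|---|---|---|
| 0.80 | 0.802 | 0.803 | 0.808 | 0.816 | 0.833 |
| 0.90 | 0.901 | 0.902 | 0.905 | 0.909 | 0.918 |
| 0.95 | 0.951 | 0.951 | 0.952 | 0.955 | 0.960 |
| 1.00 | 1 | 1 | 1 | 1 | 1 |

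Example: 0.80 / (0.95 + 0.05 × 0.80) = 0.80 / 0.99 = 0.808.

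**4. Dilution after stabilised weighting.** Weighting brings Group 3 to the pooled share of each covariate level. If affected people all sit in one level, f becomes

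fw = f × (π3 + π1 × r)

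Here r is Group 1's share of that level divided by Group 3's. π3 is Group 3's fraction of the pair from Table 5, and π1 = 1 − π3.

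- 65+: π3 = 1,351,093 / 1,733,899 = 0.779
- 18-64: π3 = 772,418 / 1,017,282 = 0.759

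At f = 5% and HR 0.80:

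| Age | r = 0 | r = 1 | r = 2 |
|---|---|---|---|
| 65+ | fw 3.90%, HR 0.806 | fw 5.00%, HR 0.808 | fw 6.10%, HR 0.810 |
| 18-64 | fw 3.80%, HR 0.806 | fw 5.00%, HR 0.808 | fw 6.20%, HR 0.810 |

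If affected people carry half the log effect (hazard multiplier √0.80 = 0.894), the range is 0.803 to 0.805. If they carry the Flu alone hazard, there is no dilution. There is also none if r = 0 and the level is added to the Cox model.

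**5. Events left after a restriction.** First, the plan's own figure for the 65+ influenza composite: (1.960 + 0.842)² / (0.23 × 0.77 × (ln 1.15)²) = 2,269 events, as stated in section 9.5. Dividing by 0.003 gives 756,333 patients, against 176,179 + 589,817 = 765,996 stated (1.3% apart).

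With Table 5 sizes, the section 9.5 event percentages, and 5% removed from both arms:

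- 65+ influenza composite: 1,733,899 × 0.003 = 5,202; × 0.95 = 4,942
- 18-64 influenza composite: 1,017,282 × 0.0009 = 916; × 0.95 = 870
- 18-64 influenza outpatient: 1,017,282 × 0.0076 = 7,731; × 0.95 = 7,345

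**The case against.** The best defence is that this is a choice and not an oversight. The study assesses only the Pfizer-BioNTech bivalent. Earlier COVID-19 vaccination of any type is a baseline covariate with its own 60-day level, so adjusting for doses before index and censoring doses after it is a recognisable approach. The word only in the section 9.1 group label may also already state the intended restriction, which would make this a matter of wording. Much of this stands, and it is why the point is minor. It does not remove the gap: the operational criteria in Table 1 do not carry out that label, and the covariate does not separate a current-season bivalent dose from an earlier monovalent one.

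A reader might infer something stronger in three ways, none of which the documents support.

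- *That the 152-day unscreened window shows a large problem.* That window belongs to an index of 30 January 2023, which contributes about one day. The longest follow-up belongs to early indexes, where every affected dose is in Recent.
- *That adjustment cannot help at all.* Balancing on the level changes the affected share. If Group 1 has nobody in the level and it enters the Cox model, the dilution disappears. The documents give no value for r.
- *That the HR is materially biased.* The only expected HR the plan states is 1, for other endpoints, and there the formula gives no shift. Residual confounding could also move the result in either direction.

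An exposure group and part of the analysis text are redacted. Whether they deal with earlier other-brand doses cannot be checked.

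**Conclusion.** The gap holds in the visible text, in both arms, and is minor. It bears on one visible result, all-cause hospitalization in Same day versus Flu alone. The expected direction is toward 1, provided the earlier dose lowers hospitalization.

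At an assumed HR of 0.80 and an affected share of 5%, the shift is at most about 0.010 for r between 0 and 2. It is smaller for an HR nearer 1 and zero at 1. A share well above 5% would enlarge it (0.833 at 20% before weighting), but nothing in the documents indicates the share. The formula counts people and not person-time, so it makes no allowance for the shorter follow-up of late indexes.

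**What to change.** Leave Table 1 and exclusion 6 as they are for Objective 1 and the descriptive tables. Table 1 defines the cohorts for every analysis, so editing it would leave these people in no visible group and alter the uptake results. Add to section 9.7 instead:

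*The Same day versus Flu alone effectiveness models will be restricted, in both groups, to people with no claim for another brand's mRNA bivalent COVID-19 vaccine from 31 August 2022 to the day before index. The number removed will be reported by group and age.*

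The rule uses only information from before index and treats both arms alike, and any-brand bivalent claims must already be identified for censoring. The count reported for Flu alone replaces the unknown f.

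The cost is a line of cohort code and a modest loss of patients in one comparison. If 5% of both groups is removed, the 65+ influenza composite keeps about 4,942 expected events against 2,269 needed, and the 18-64 influenza outpatient endpoint about 7,345 against 2,269. The 18-64 influenza composite, already short, falls from about 916 to 870. The effect on power for all-cause hospitalization cannot be computed, because section 9.5 gives no event rate for it. Group 1 versus Group 2 is unchanged.

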9.3. Variables

9.3.1. Exposure

Table 1. Vaccination Status Variables		
Variable	Role	Operational definition
Group 1: Same Day (Concomitantly administered Pfizer-BioNTech COVID-19 mRNA bivalent vaccine + influenza vaccine)	Exposure	
Patients meeting the following criteria will be included in the Same Day cohort:
 
1. NDC or CPT codes for both the Pfizer-BioNTech mRNA bivalent COVID-19 vaccine and an influenza vaccine during the study period.2. The first Pfizer-BioNTech mRNA bivalent COVID-19 vaccine and influenza vaccine NDC or CPT codes during the study period occurred on the same date.3. No influenza vaccine NDC or CPT code between 01 August 2022 and 30 August 2022. 
If the patient receives >1 mRNA bivalent COVID-19 vaccine or influenza vaccine during follow-up, the patient is censored on the date of the NDC or CPT code for the second vaccine of the same type. mRNA bivalent COVID-19 and influenza vaccine NDC and CPT codes are listed in Appendix Table 1.

Group 2: COVID alone (COVID-19 mRNA bivalent vaccine alone)	Exposure	
Patients meeting the following criteria will be included in the COVID-19 alone cohort:
 
1. Pfizer-BioNTech mRNA bivalent COVID-19 vaccine NDC or CPT code during the study period and no influenza vaccine on that date.2. No influenza vaccine NDC or CPT code between 01 August 2022 and 30 August 2022. 
If the patient receives >1 mRNA bivalent COVID-19 vaccine (any type) during follow-up or an influenza vaccine, the patient is censored on the date of the NDC or CPT code for the second mRNA bivalent COVID-19

PFIZER CONFIDENTIAL

Table 1. Vaccination Status Variables

Variable	Role	Operational definition
		vaccine/influenza vaccine. mRNA bivalent COVID-19 vaccine NDC and CPT codes are listed in Appendix Table 1 .
Group 3: Flu alone (Influenza vaccine alone)	Exposure	
Patients meeting the following criteria will be included in the Flu alone cohort:
 
1. Influenza vaccine NDC or CPT code during the study period and no mRNA bivalent COVID-19 vaccine on that date.2. No influenza vaccine NDC or CPT code between 01 August 2022 and 30 August 2022. 
If the patient receives >1 influenza vaccine or an mRNA bivalent COVID-19 vaccine (any type) during follow-up, the patient is censored on the date of the NDC or CPT code for the second influenza vaccine/COVID-19 vaccine. Influenza vaccine NDC and CPT codes are listed in Appendix Table 1.

CCI		[REDACTED]

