8. RESEARCH QUESTION AND OBJECTIVES

Primary Objective 1: To describe the proportion of Pfizer-BioNTech bivalent mRNA COVID-19/influenza vaccines that are concomitantly administered, and the characteristics of patients who receive concomitant administration.

Primary Objective 2: To estimate vaccine effectiveness (VE) of concomitant administration of a single dose of the mRNA Pfizer-BioNTech bivalent COVID-19 vaccine and a licensed flu vaccine versus either vaccine alone against all-cause hospitalization or acute respiratory illness requiring hospitalization, emergency department/urgent care or outpatient encounters.

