9.3.2. Outcomes

All outcomes will be assessed starting on Day 15. All hospitalization related outcomes in the table below will be ascertained using acute facility stays only. Inpatient stays classified as skilled nursing facility or rehabilitation will not be used. COVID-19 and flu hospitalizations will be assessed in any position and in the primary position to mitigate possibility of hospitalization with the disease versus for the disease.

COVID-19 related endpoints will be identified using the following ICD-10-CM diagnosis code: U07.1.

Influenza will be identified using the following ICD-10-CM diagnosis codes: J09.X, J10.X, J11.X.

We will evaluate three negative control outcomes. These outcomes are unrelated to vaccination and likely share similar confounding patterns for health-seeking behaviors. These negative controls have been used in other studies of comparative VE of influenza vaccines or COVID-19 VE.¹³⁻¹⁵ Urinary tract infection and accidental injury are outcomes that could differentiate patients who seek medical care versus those who do not, and is likely a better choice of outcome for younger adults. Hospitalization in the first 14 days (ie, among recently vaccinated) uses time as a negative control, in that the vaccine likely could not biologically prevent health events until adequate levels of immunity has been achieved.

Table 2. Outcome Variables

Variable	Role	Operational definition
All-cause hospitalization	Outcome	An inpatient (acute facility) claim that meets the following criteria: 
1. Occurs >14 days after the patient's first mRNA bivalent COVID-19 or influenza vaccine dose during the study period.2. Place of service = 21.3. Non-null confinement ID.4. tos_cd = 'FAC_IP.ACUTE'.
Composite COVID-19 related hospitalization/ED/UC (any position)	Outcome	An inpatient (acute facility) claim that meets the following criteria: 
1. Occurs >14 days after the patient's first mRNA bivalent COVID-19 or influenza vaccine dose during the study period.2. Place of service = 21.

PFIZER CONFIDENTIAL

Table 2. Outcome Variables

Variable	Role	Operational definition

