Urinary tract infection	Negative control outcome	≥1 ICD-10-CM diagnosis code in any position/any setting for a urinary tract infection (that occurs >14 days after the patient's first mRNA bivalent COVID-19 or influenza vaccine dose during the study period).
Accidental injury	Negative control outcome	≥1 ICD-10-CM diagnosis code in any position/any setting for accidental injury that occurs >14 days after the patient's first mRNA bivalent COVID-19 or influenza vaccine dose during the study period.
Hospitalization in the 14 days following vaccination (recently vaccinated) Day 1-14	Negative control outcome	
An inpatient (acute facility) claim that meets the following criteria:
 
 1. Occurs ≤14 days after the patient's first mRNA bivalent COVID-19 or influenza vaccine dose during the study period.

PFIZER CONFIDENTIAL

Table 2. Outcome Variables

Variable	Role	Operational definition
		2. Place of service = 21. 3. Non-null confinement ID.
CCI		
CCI		
CCI		
CCI		

PFIZER CONFIDENTIAL

Table 2. Outcome Variables

Variable	Role	Operational definition
		within 60 days following discharge.
CCI [REDACTED]	[REDACTED]	[REDACTED]
Follow-up time	Outcome descriptive	Measured from day 15 through the minimum date of censoring (see follow-up time description in Section 9.3.3). Mean, standard deviation (SD), median (Q1-Q3), minimum, and maximum, will also be summarized for the length of follow-up in each group.

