9.3.3. Censoring

The censoring date will be the minimum date in follow-up (starting >14 days after vaccination) of the following variables.

Table 3. Censoring Variables

Variable	Role	Operational definition
Outcome under study	Censoring	See outcome table above. Table 2 .
Disenrollment	Censoring	Date a patient disenrolls from the insurance plan, as indicated in the enrollment file.
End of data	Censoring	14 February 2023
Receipt of second vaccine of the same type	Censoring	Any kind of mRNA bivalent COVID-19 vaccine is considered as a censoring vaccine. See exposure table for vaccination definitions.
Receipt of the other vaccine type	Censoring	Any kind of mRNA bivalent COVID-19 vaccine is considered as a censoring vaccine. See exposure table for vaccination definitions.
Death	Censoring	Death date is assigned the midpoint of the month in which death is reported in the database.
Nirmatrelvir/ritonavir (sensitivity analysis for COVID-19 endpoints)	Censoring	First dispensing for Nirmatrelvir/ritonavir during follow-up using NDC codes.
Influenza treatment (sensitivity analysis for treatment endpoints)	Censoring	First dispensing of any influenza treatments (see outcome table above for definitions) during follow-up using NDC codes.

PFIZER CONFIDENTIAL

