9.5. Study Size

The sample size for this study is fixed by the duration of the observation window. All subjects who meet the inclusion/exclusion criteria will be included in the analyses.

Feasibility analyses from 31 August 2022- 16 January 2023 confirmed the availability of data to identify vaccinated subjects. Table 5 below shows the estimated number of patients in each group.

Table 5. Estimated Number of Patients in Each Vaccination Exposure Group

	Group 1: Same Day	Group 2: COVID- 19 alone	Group 3: Flu alone	CCl [REDACTED]
18-64	244,864	144,695	772,418	CCl [REDACTED]
65+	382,806	225,842	1,351,093	CCl [REDACTED]

Composite COVID-19 hospitalizations/UC/ED

For 65+, and the Group 1 vs Group 2 comparison of the COVID-19 related composite hospitalizations/ED/UC endpoint, we assume the percentage of patients in Group 1 will be 63% and the expected percentage of patients in Group 1 and Group 2 with an event overall will be 0.56%. If we use a non-inferiority margin of 1.15 for the upper bound of the 95% CI, 1-sided alpha of 0.025, and 80% power, and an expected HR of 1, then we would need 1,724 events resulting in 193,548 patients in Group 1, and 113,671 in Group 2, which meets our current estimated sample size.¹⁹

For 18-64, and the Group 1 vs Group 2 comparison of the COVID-related composite hospitalizations/ED/UC endpoint, we assume the percentage of patients in Group 1 will be 63% and the expected percentage of patients in Group 1 and Group 2 with an event overall will be 0.066%. If we use a non-inferiority margin of 1.15 for the upper bound of the 95% CI, 1-sided alpha of 0.025, and 80% power, and an expected HR of 1, then we would need 1,638,003 in Group 1, and 962,002 in Group 2, which does not meet our current estimated sample size.

Composite influenza hospitalizations/UC/ED

For 65+ and for the Group 1 vs Group 3 comparison of the flu-related composite hospitalizations/UC/ED endpoint, we assume the percentage of patients in Group 1 will be 23% and the expected percentage of patients in Group 1 and Group 3 with the endpoint overall will be 0.3%. If we use a non-inferiority margin of 1.15 for the upper bound of the 95% CI, 1-sided alpha of 0.025, and 80% power, and an expected HR of 1, then we would need 2,269 events resulting in 176,179 in Group 1, and 589,817 in Group 3, which meets our current estimated sample size.

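### Censoring at the other vaccine can occur only in the single-vaccine groups, while the readable analysis balances covariates only at index; a pre-specified sensitivity analysis would show whether this matters

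*Combined protocol and SAP*

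**What the plan says.** Section 9.1 follows patients from day 15 and counts among the events that end follow-up "receipt of the other vaccine or any type of COVID-19 vaccine". Table 1 (Section 9.3.1) applies this to Group 2, "If the patient receives >1 mRNA bivalent COVID-19 vaccine (any type) during follow-up or an influenza vaccine, the patient is censored", and to Group 3, "If the patient receives >1 influenza vaccine or an mRNA bivalent COVID-19 vaccine (any type) during follow-up, the patient is censored". Table 3 (Section 9.3.3) repeats it in the row "Receipt of the other vaccine type". In Group 1, vaccination censors only at a second vaccine of the same type.

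Primary Objective 2 (Section 8) compares concomitant administration "versus either vaccine alone against all-cause hospitalization" and respiratory endpoints, so stopping follow-up at the other vaccine fits the question.

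In Section 9.7, covariates from baseline or the index date feed a propensity score for index exposure. Balance is checked before and after weighting, only covariates that remain imbalanced enter the outcome model, and ordinary Cox models give the HRs. The readable sensitivity analysis adds censoring at antiviral dispensing.

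Two features could give partial warning. Of the negative controls, Section 9.3.2 says "These outcomes are unrelated to vaccination and likely share similar confounding patterns for health-seeking behaviors"; urinary tract infection and injury are counted in the same window as the main outcomes. Summary statistics "will also be summarized for the length of follow-up in each group". The limitations in Section 9.9 do not mention informative censoring.

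**The concern.** Weighting makes the groups alike on day 15. From then on, Groups 2 and 3 lose people who take the other vaccine, and Group 1 loses nobody for that reason. Suppose a covariate is balanced at index but makes later uptake more likely. It passes the balance check and therefore stays out of the Cox model, yet its share among comparators still at risk drifts away from its share in Group 1. If it also predicts the outcome, the later risk sets are no longer comparable.

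If lower-risk people take the second vaccine sooner, the remaining comparators are higher-risk and same-day vaccination looks better than it is. If higher-risk people do, it looks worse. This bias does not shrink as the sample grows, so it matters most for endpoints with many events. These two comparisons are the readable analysis of Primary Objective 2.

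**Working it through.** **1. The plan's own figure.** Section 9.5 uses margin 1.15, one-sided alpha 0.025, 80% power and a 63:37 split. Events = (1.96 + 0.8416)² / [0.63 × 0.37 × (ln 1.15)²] = 1,724, as stated. With 23:77 the result is 2,269, also as stated. The size calculation is not in question.

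**2. Bias model.** The documents give no crossover rate and no predictor of crossover, so every input here is assumed:
- true HR 1 and rare events;
- one binary factor, prevalence π of 30-50%, balanced at index;
- Group 1 share 0.63 or 0.23 (Section 9.5);
- administrative follow-up uniform over 0-152 days (31 August index plus 15 days, to 14 February, is 152 days);
- crossover c defined as the cumulative probability by day 152, with hazard λ = -ln(1 - c)/152.

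The prevalence of the factor among comparators at risk on day t is q(t) = πe^(-λ₁t) / [πe^(-λ₁t) + (1 - π)e^(-λ₀t)]. In Group 1 it stays π. With outcome HR R for the factor, the apparent HR on day t is [1 + (R - 1)π] / [1 + (R - 1)q(t)]. The Cox HR averages this over follow-up and was found by solving the score equation.

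**3. Worked example.** Take π = 0.40, R = 2, share 0.63, and crossover 25% with the factor and 50% without. Then λ₁ = 0.00189 and λ₀ = 0.00456 per day.
- Day 60: q = 0.439, apparent HR = 1.4/1.439 = 0.973.
- Day 120: q = 0.479, apparent HR = 1.4/1.479 = 0.947.
- Cox HR over follow-up: 0.978. With the two crossover rates swapped: 1.022.
- Equal crossover, or R = 1: 1.000.

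Few people reach day 152, so the share actually censored is smaller than c. Per stratum it is 1 - c/[-ln(1 - c)], which is 13.1% for c = 0.25 and 27.9% for c = 0.50. Here that gives 0.4 × 13.1% + 0.6 × 27.9% = 22%.

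**4. Grid.**

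| Crossover by day 152 | Comparators actually censored | Outcome HR of factor | Cox HR (truth 1) |
|---|---|---|---|
| 30% vs 15% | 10-13% | 1.5-2 | 0.989-0.994 or 1.006-1.011 |
| 50% vs 25% | 18-23% | 1.5-2 | 0.978-0.988 or 1.011-1.023 |
| 60% vs 20% | 18-27% | 2-3 | 0.941-0.965 or 1.034-1.061 |

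**5. Effect on coverage.** Events = Table 5 patients × the event proportion in Section 9.5. SE = 1/√[events × share × (1 - share)]. Coverage = Φ(1.96 - ln HR/SE) - Φ(-1.96 - ln HR/SE).

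| Endpoint | Events | SE | Coverage at 0.99/1.01 | Coverage at 0.98/1.02 |
|---|---|---|---|---|
| 65+ COVID-19 composite | 608,648 × 0.56% = 3,408 | 0.0355 | 94% | 91% |
| 65+ influenza composite | 1,733,899 × 0.3% = 5,202 | 0.033 | 94% | 91% |
| 65+ COVID-19 outpatient | 608,648 × 1.77% = 10,773 | 0.020 | 92% | 83% |
| 18-64 COVID-19 composite | 389,559 × 0.066% = 257 | 0.129 | 95% | 95% |

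Section 9.5 gives no event proportion for all-cause hospitalization, so it is not calculated here.

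**6. Would the planned outputs reveal it?** Follow-up length alone would not. Mean comparator follow-up is 69.0-70.7 days with 30% vs 15% crossover and 69.9 days with equal 22.5% crossover. Standardized differences among those still at risk do move: from 0 at index to about 0.04 (30% vs 15%) or 0.07-0.08 (50% vs 25%) by day 60 of follow-up. That shows the factor drives uptake, not that it predicts the outcome.

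**The case against.** The strongest reply is that this is conditional and may be negligible. It needs two links, its direction is open, and opposing drivers could cancel. In the milder rows of the grid the bias is 1-2%, small beside the 1.15 margin, and the powered 65+ composites keep 91-94% coverage. The negative controls in the same window might reveal part of it. Exclusion criterion 1, if it covers the other vaccine, also removes crossovers in the first 14 days. All of this stands, and it limits the severity. It does not remove the point: later crossovers remain, the controls correct nothing, and the readable text gives no rule for acting on them.

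Some stronger readings are tempting but unsupported:
- A reader might infer that the plan favours same-day vaccination. The documents say nothing about who crosses over, so the direction is open.
- A reader might take 1-2% as a ceiling. It holds only for the milder assumed inputs; 60% vs 20% crossover gives 3-6%.
- A reader might treat drift in balance as proof of bias. Both links are needed.
- A reader might conclude that the sponsor planned nothing. A further exposure group, rows of Table 2 and a block in Section 9.7 are redacted, so the statement covers the readable text only.

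**Conclusion.** The point holds in conditional form. Other-vaccine censoring is one-sided by design, and the readable analysis neither adjusts for it nor examines it after index. A measured baseline covariate that drives uptake and predicts the outcome would bias the HR if the plan were followed exactly. Neither the size nor the direction can be settled from the documents, and the figures above rest wholly on assumed crossover and risk inputs. The consequence is greatest for the precise 65+ estimates and slight for the 18-64 COVID-19 composite. The censoring rule itself is not an error. This is a cheap improvement of low to moderate severity.

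**What to change.** Keep the censoring rule and the primary analysis. In Section 9.7, pre-specify a sensitivity analysis for other-vaccine censoring, shown beside the primary result, by one or both of these routes:
- **Simplest:** the IPTW Cox model further adjusted for the Table 4 model covariates. In a simulated check with one driver, adjustment brought the HR back to 0.987-1.000 (Monte Carlo SE about 0.01).
- **Alternative:** IPTW multiplied by stabilized inverse-probability-of-censoring weights for receipt of the other vaccine in Groups 2 and 3, from a weekly pooled logistic model on the Table 4 covariates, with robust variance. Two comparators by two age strata makes four weight models. In simulation with one correctly modelled driver (50% vs 25%, outcome HR 2), 0.981 became 1.001 and 1.025 became 1.004.

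Report the number and timing of other-vaccine censorings by group and age stratum. Report weighted standardized differences among those still at risk at set times (for example days 30, 60, 90 and 120 of follow-up). Give them as values, since a 0.1 cut-off would miss the milder case, and describe them as evidence of what drives uptake rather than as proof of bias.

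In Section 9.9, list informative censoring and say that baseline covariates cannot correct for unmeasured or post-index drivers.

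The cost is extra programming on covariates already built, two tables and, with weights, somewhat wider intervals. Person-week data for Groups 2 and 3 will be large. The correction is partial: with two equal drivers and only one in the weights, about half of the bias remains (0.969 becomes 0.985).
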